6.1. Screening for Eligibility

Potential participants will either contact the research staff directly or will be referred by their physician. Upon initial contact the research staff member will ascertain interest in participating in the study by providing a study description that references the procedures involved in the study and expected timeline. If the potential participant would like to continue, the research staff member will review the inclusion/exclusion criteria to determine eligibility. This initial screening can be conducted in person or over the phone, using the phone script available on the

study website. If the potential participant is eligible, the research staff member either will provide a copy of the informed consent for the potential participant to review or will proceed to schedule a time for the participant to come to the clinic to review the informed consent. Please see Section 5.3.3 for details on the consent process.

6.2. Schedule of Measurements

Table 3. Schedule of Study Measurements

	V1	V2	V3	V4
Physiological Measures				
Pulmonary Function Testing				
Exhaled CO (eCO)	X	X		X
Forced Vital Capacity	X	X	X	X
Slow vital capacity	X	X	X	X
Bronchodilation	X	X	X	X
Forced Vital Capacity	X	X	X	X
Slow Vital Capacity	X	X	X	X
Six minute walk test with continuous pulse oximetry	X	X	X	X
Anthropometric Measurements				
Height	X	X	X	X
Weight	X	X	X	X
Arm Span	X	X	X	X
Waist	X	X	X	X
Hip	X	X	X	X
Neck	X	X	X	X
Seated Blood Pressure	X	X	X	X
MDCT	X	X		
Biospecimen collection				
Blood				
Serum (Two - RT)	X	X		X
Plasma (One - P100)	X	X		X
Plasma (Three - Plasma/DNA w/EDTA and One CBC w/EDTA)	X	X		X
Plasma (One –with citrate)	X	X		X
RNA (One – PAX - Gene)	X	X		
Urine	X	X		X
Induced Sputum	X	X*	X*	X*
Questionnaires				
Medical History	X	X	X	X
St. George’s Respiratory Questionnaire	X	X	X	X
MOT Short Form – 12	X	X	X	X
COPD Assessment Test	X	X	X	X
Modified Medical Research Council (MRC) Dyspnea Scale	X	X	X	X
Sleep questionnaires				
Berlin Questionnaire	X	X	X	X
Pittsburgh Sleep Quality Index	X	X	X	X
Veterans Specific Activity Questionnaire	X	X	X	X
Hospital Anxiety and Depression Scale (HADS)	X	X	X	X
FACIT	X	X	X	X
Questionnaire for Ease of Cough and Sputum Clearance	X	X	X	X

*Sample collection attempted only if initial collection at baseline failed.

6.3. Study Visit Scheduling

The procedures and assessments for primary study visits, i.e., Baseline, Year 1, Year 2, and Year 3, may take place over multiple days as long as all procedures are completed within 42 days of the start of a particular visit.

6.4. Description of Study Exams, Specimen Collection, and Questionnaires

6.4.1. Pulmonary Function Tests

6.4.1.1. Background and Rationale

The 2005 ATS/ERS guidelines for pulmonary function testing and interpretation will serve as the primary guidance for the conduct and interpretation of the spirometry measurements (Macintyre et al, 2005; Miller et al, Jul 2005; Miller et al, Aug 2005; Pellegrino et al, 2005; Wanger et al, 2005). The 2002 ATS statement will guide the six-minute walk test (ATS Statement, 2002).

The between-maneuver repeatability, which 90% of consecutive patients can meet, is 120 ml (6.1%) for FEV₁ and 150 ml (5.3%) for FVC (Enright et al, 2004). The established target is 150 ml for both measures (or 100 ml if the FVC is <1 L) (Miller et al, Aug 2005). The short-term (24.9±17.1 days) reproducibility in mild COPD participants is 113 ml (CV 4.1%) for FEV₁ and 150 ml (CV 3.5%) for FVC (10). The minimal clinically significant difference for FEV₁ is about 100 ml (Donohue et al, 2004).

6.4.1.2. Inclusion/exclusion specific to procedure

6.4.1.2.1. Inclusion criteria

There are no additional inclusion criteria for the PFT procedures.

6.4.1.2.2. Exclusion criteria

For six-minute walk, clinically significant cardiac, orthopedic or balance difficulties or resting hypoxemia (S_pO₂ <88% on room air, may be modified for altitude) are reasons for exclusion.

6.4.1.2.3. Notes related to inclusion/exclusion criteria specific to pulmonary function testing

Reversibility is neither an inclusion or exclusion criteria.

6.4.1.3. Methods

A central training session will be conducted prior to the start of enrollment. Pulmonary function technicians at each clinical center will have to be trained in the skills necessary to use the study specific equipment and methods. All technicians will be certified prior to data collection, with recertification annually.

Spirometry (SVC and FVC) will be performed on standardized equipment. Centralized quality assurance will be used.

Following is the brief testing sequence and methods for each visit (baseline, year 1, year 2, and year 3):

Prior to PFTs, participants will be asked to withhold/refrain from vigorous exercise (0.5 hours), smoking (1 hour), eating a large meal (2 hours), alcohol (4 hours), caffeine (6 hours), inhaled albuterol (6 hours), inhaled ipratropium (8 hours), and any other bronchodilators for 24 hours. Practicality may require some long-acting bronchodilators to simply be noted rather than withheld. Instructions for withholding bronchodilator medications prior to testing will stress the continued use of rescue medication if needed. The use of albuterol or ipratropium will generally relieve any symptoms related to the trough effect of long-acting bronchodilators. Failing to withhold/refrain from the above activities will not exclude a participant from continuing with PFTs.

Data will be collected in the following order:

- 1) Slow vital capacity (expiratory vital capacity method), including measurement of inspiratory capacity after a stable (at least 3 breaths) end-expired volume
- 2) Forced vital capacity
- 3) Bronchodilation with albuterol sulfate HFA and ipratropium bromide HFA four puffs each (30 minute waiting period before post-bronchodilator SVC or FVC)
- 4) Slow vital capacity, 30-120 minutes post bronchodilator (expiratory vital capacity method)
- 5) Forced vital capacity, 30-120 minute post bronchodilator
- 6) Six-minute walk test with continuous oximetry recording. S_pO_2 will be recorded every 2 seconds on a pulse oximeter. The test will be stopped if the S_pO_2 declines to <80%.

6.4.1.4. Bronchodilator dosing and re-dosing

The study dose of bronchodilators for post-bronchodilator spirometry is 4 puffs of ipratropium and 4 puffs of albuterol. If bronchodilators are used at home prior to the study visit, the dose is recorded on the Pulmonary Function Test Form (PFT Form, see study website). The use of bronchodilators at home prior to the visit does not change the study dose during spirometry. Participants may take their usual medications approximately 165 minutes after completing the post-bronchodilator spirometry.

Re-dosing of one or both bronchodilators is required prior to the six minute walk, CT, or sputum induction, if too much time has elapsed since the last puff of albuterol taken for post-bronchodilator spirometry. Table 4 provides the requirements for re-dosing for CT scan and six minute walk.

Table 4. Bronchodilator Dosing and Re-dosing Schedule for CT Scan and Six Minute Walk Conducted on the Same Day as Study Spirometry

Time after initial dose	Administer	Test by
< 165 minutes	No additional puffs	30-180 minutes after original doses
Participant takes usual medications approximately 165 minutes after post-bronchodilator spirometry		
>-165 and <300	2 puffs albuterol	15-180 minutes after new albuterol
>=300 minutes	2 puffs of ipratropium and 2 puffs albuterol	30-180 minutes after new albuterol

If the CT scan or six minute walk occurs on a separate day from the spirometry, then the participant should be instructed to take their medications as usual (i.e., no withholding), and should be dosed with 2 puffs of albuterol and 2 puffs of ipratropium.

For induced sputum, if COPD subjects have not had albuterol in the prior 165 minutes, regardless of whether the induction occurs on the same day as the study spirometry, then they should be dosed with 2 puffs of albuterol. Participants who are non-smokers or smokers without obstruction do not need albuterol for the sputum induction. The investigator should be contacted if a participant reports having asthma and would otherwise not receive albuterol.

6.4.1.5. Justification for the use of both albuterol and ipratropium to measure the response to a bronchodilator and determine the post-bronchodilator FEV₁, FVC and SVC (including inspiratory capacity)

The standard of practice in the community for assessing the response to a bronchodilator involves the performance of spirometry before and 15-30 minutes following administration of 2-3 inhalations of albuterol sulfate HFA (90 mcg/inhalation). However, according to the current GOLD guidelines (2008), “possible dosage protocols are 200 mcg β_2 -agonist, up to 160 mcg anticholinergic or the two combined with repeat measurement of FEV₁ 10-15 minutes after the β_2 -agonist or 30-45 minutes after the combination” (GOLD Executive Committee, 2008).

According to the SPIROMICS protocol, spirometry will be performed before and 30-120 minutes following administration of 4 inhalations of albuterol sulfate HFA plus 4 inhalations of ipratropium bromide HFA (17 mcg/inhalation). The rationale for using the two different classes of short-acting inhaled bronchodilators (beta-adrenergic agonist plus anticholinergic) in twice the usual recommended therapeutic dose for assessing the bronchodilator response is based on well-established evidence of the additive bronchodilator effect of the two different types of inhaled bronchodilators (Dorinsky et al, 1999). Similarly, the reason for administering 4, rather than the conventional 2, inhalations of each bronchodilator is based on evidence that, in general, maximal bronchodilation is not achieved with only 2 inhalations of either agent (Harrison et al, 1983; Gross et al, 1989).

In SPIROMICS, pre- and post-bronchodilator spirometry will be performed both for assessing the degree of bronchodilator responsiveness and for determining the post-bronchodilator FEV₁, FVC and SVC (including IC). The degree of bronchodilator responsiveness may be considered a surrogate for airway responsiveness to methacholine, is a potential determinant of disease progression (as measured by the annual rate of change in FEV₁) (Anthonisen, Wright, et al, 1986; Tashkin et al, 1996) and may also help define a COPD phenotype, namely one characterized by pronounced versus minimal reversibility of airflow obstruction. The post-bronchodilator FEV₁ is the metric that has traditionally been used to define disease progression in COPD (Anthonisen et al, 1994) since it tends to minimize the day-to-day variability in pre-bronchodilator FEV₁ that is largely related to day-to-day variability in bronchomotor tone. SPIROMICS will rely on administering 4 inhalations of both a beta-agonist and an anticholinergic bronchodilator in an effort to optimize our ability 1) to determine maximal bronchodilator responsiveness and 2) to obtain reproducible values of FEV₁ (unconfounded by varying bronchomotor tone), thus affording greater precision in assessing the annual rate of decline in FEV₁.

The bronchodilator reversibility procedure employed in SPIROMICS, although different from what is currently the standard of practice, has the potential for setting a new standard for determining reversibility of airflow obstruction and hyperinflation, in addition to providing a more reliable measure of disease progression, as defined by the annual decline in lung function.

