CT scans should be conducted after the participant has received the bronchodilator dose administered for post-bronchodilator spirometry. For CT scans occurring on the same day as spirometry, if the scan occurs more than 165 minutes after the last dose of bronchodilation, then the participant will need to be re-dosed as described in Section 6.4.1.4 and Table 4.

If the CT scan occurs on a separate day from spirometry, subjects should not withhold bronchodilators prior to the study visit for the CT scan. Subjects will receive 2 puffs of albuterol and 2 puffs of ipratropium before the CT scan as described in Section 6.4.1.4.

At all visits subsequent to the baseline visit, participants will be scanned at the same dose as was used during the baseline CT visit unless either 1) the original scan was at a higher than appropriate dose (e.g., small subject scanned as a medium) or 2) the participant's BMI has changed more than three units on either side of the BMI thresholds for dose categories.

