6.4.4.4. Measurements

1) Primary candidate outcomes / phenotype measures:

- Volume measures (assessed for whole lung, left and right lung and lung lobes):
- Total volume at TLC and RV
- Total air volume at TLC and RV
- Total tissue (non-air) volume at TLC and RV

Primary parenchymal measures to be assessed from the TLC scans on a per lung, right and left lung, and lobar basis in this study are:

- Lower 15th percentile point (in Hounsfield Units: HU) of the lung density histogram assessed from TLC scans at baseline and the rate of leftward shift over time.
- Percent of voxels below -950, -910, 850, and their change over time.
- “Alpha” assessed for holes defined as connected voxels whose values fall below -950 HU.

Primary parenchymal measure to be assessed from the RV scans on a per lung, right and left lung and lobar basis in this study are:

- Percent of lung voxels below -850. (index of air trapping) and its change over time.

Primary airway measures to be assessed at each airway segment out to 6 generations (as detectable) along 6 paths (RB1, RB4, RB10, LB1, LB4, and LB10)

- Luminal area at baseline and over time
- Luminal perimeter at baseline and over time
- Average wall thickness at baseline and over time
- Wall area percent at baseline and over time

2) Secondary outcomes / phenotype measures:

These measures are less well tested in the literature and will be performed in an attempt to evaluate their utility in the identification of COPD phenotypes and disease progression.

Secondary parenchymal measures to be assessed from the TLC scans:

- Parenchymal measures assessed for sub-lobar (areas of influence of primary lobar airways) segments including change over time
- Raw texture measures on a lobar and sub-lobar basis including change over time

Secondary parenchymal measures to be assessed from the RV scans:

- Percent of voxels falling below -850 evaluated for sub-lobar segments and the change over time
- Pulmonary artery vascular volume assessed for the arterial volume within the borders of the lung out to the 5th generation pulmonary arteries and the change over time

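### Nothing ties a participant's bronchodilator condition at the Year 1 CT to the one at baseline, so change in air trapping and airway size can be confounded where the two differ

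*Protocol*

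**What the plan says.** **Same day as spirometry.** Section 6.4.1.3 asks participants to withhold "inhaled albuterol (6 hours), inhaled ipratropium (8 hours), and any other bronchodilators for 24 hours", while accepting that some long-acting drugs may only be documented. Section 6.4.1.4 then fixes the dose: "The study dose of bronchodilators for post-bronchodilator spirometry is 4 puffs of ipratropium and 4 puffs of albuterol". A CT or walk soon afterwards needs no further puffs. Table 4 adds 2 puffs of albuterol from 165 to under 300 minutes, and "2 puffs of ipratropium and 2 puffs albuterol" from 300 minutes. Usual medication may be taken at about 165 minutes.

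**Separate day.** Section 6.4.1.4 states that "the participant should be instructed to take their medications as usual (i.e., no withholding), and should be dosed with 2 puffs of albuterol" and 2 of ipratropium. Section 6.4.4.3 repeats this for the CT.

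**Scheduling.** Under section 6.3 the procedures of a visit "may take place over multiple days as long as all procedures are completed within 42 days".

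**Matching between visits.** Section 6.4.4.3 says "participants will be scanned at the same dose as was used during the baseline CT visit", with two exceptions. That rule concerns radiation dose. No corresponding rule covers the bronchodilator condition.

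**Use of the measurements.** Section 6.4.4.4 lists air trapping on the RV scan with its change over time, and airway measures such as "Luminal area at baseline and over time", among the primary candidate CT measures. Table 3 schedules CT only at baseline and Year 1. Section 7.4.3 gives baseline-to-Year-1 change as one example of an intermediate outcome.

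**Stated rationale.** Section 6.4.1.5 supports 4 puffs on the ground that, in general, "maximal bronchodilation is not achieved with only 2 inhalations of either agent". It adds that the fixed dose keeps changes in airway tone from distorting FEV1, which sharpens the estimate of annual decline.

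**The concern.** The protocol controls airway tone carefully for FEV1 because FEV1 is read as change. Air trapping and airway lumen and wall dimensions are also to be read as change, and may also depend on airway tone, but for them the condition is left to scheduling and elapsed time.

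Each participant has two CT scans and hence one CT change score. If the baseline scan followed spirometry on the same day and the Year 1 scan was on another day, any effect of the condition enters that score in full, and no third scan can reveal it. If such switches are haphazard, they add noise and weaken correlations with three-year endpoints. If they run mainly one way, they shift mean change. If they run one way more often in some participants than in others, they bias the comparison between those groups.

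The walk is a secondary matter. It is the last step of the lung-function sequence in section 6.4.1.3, so same-day testing is its normal setting, and it is measured at all four visits. Exercise endurance does, however, enter the BODE index, which section 4.1.3.1 uses as a Year 3 endpoint.

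**Working it through.** The plan states no figure on this point, so there is none to reproduce.

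**Step 1: conditions side by side (sections 6.4.1.3, 6.4.1.4, 6.4.4.3)**

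| Timing of CT or walk | Background medication | Study puffs (albuterol + ipratropium) |
|---|---|---|
| Same day, under 165 min | withholding requested | 4+4 |
| Same day, 165 to under 300 min | usual medication may have been taken | 4+4, then 2 albuterol |
| Same day, 300 min or later | usual medication may have been taken | 4+4, then 2+2 |
| Separate day | usual medication, not withheld | 2+2 |

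At the strengths quoted in section 6.4.1.5 (90 mcg and 17 mcg per inhalation), the initial same-day dose is 4 × 90 = 360 mcg albuterol and 4 × 17 = 68 mcg ipratropium. The separate-day dose is 2 × 90 = 180 mcg and 2 × 17 = 34 mcg. That is half the study dose, but on top of unwithheld usual medication. The conditions therefore differ in dose, background and timing; the net difference in bronchodilation, including its sign, cannot be derived.

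**Step 2: is anything held constant between visits?** The one matching rule for CT covers scan dose. The covariates named in section 7.4.3 (gender, height, weight, clinical site) do not include bronchodilator condition, but the list is open.

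**Step 3: illustration. Every input here is an assumption.** Treat the arrangement as two states, same-day or separate-day. Let d be the effect of the condition in SD of one-year change, and p0 and p1 the separate-day shares at baseline and Year 1, independent between visits.

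- Share switching = p0(1−p1) + p1(1−p0)
- Shift in mean change = (p1−p0)·d
- Added variance = [p0(1−p0) + p1(1−p1)]·d²
- Factor on correlations = 1/√(1 + added variance)

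With p0 = p1 = p, the share switching is 2p(1−p): 18% at p = 0.1, 32% at 0.2, 42% at 0.3 and 50% at 0.5.

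| p0, p1 | d | Mean shift (SD) | Added variance | Factor on correlations |
|---|---|---|---|---|
| 0.5, 0.5 | 0.1 | 0 | 0.005 | 0.998 |
| 0.5, 0.5 | 0.2 | 0 | 0.020 | 0.990 |
| 0.5, 0.5 | 0.5 | 0 | 0.125 | 0.943 |
| 0.2, 0.5 | 0.1 | 0.03 | 0.0041 | 0.998 |
| 0.2, 0.5 | 0.2 | 0.06 | 0.0164 | 0.992 |
| 0.2, 0.5 | 0.5 | 0.15 | 0.1025 | 0.952 |

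For example, at p0 = 0.2, p1 = 0.5 and d = 0.5, the shift is 0.3 × 0.5 = 0.15 and the added variance is (0.16 + 0.25) × 0.25 = 0.1025.

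**Step 4: the limits.** If every participant keeps the same arrangement, the scheduling contribution to change is zero. If everyone moves from same-day to separate-day, mean change shifts by the full d. If arrangements persist within participants with correlation r, the share switching falls to 2p(1−p)(1−r); at p = 0.3 and an assumed r = 0.5 this is 0.42 × 0.5 = 21%.

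**The case against.** Several points against the concern stand.

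- Sections 6.4.1.4 and 6.4.4.3 agree on the separate-day rule. They do not contradict each other.
- A condition held constant within a participant largely cancels. A reader might infer that CT change always mixes drug effect with disease; the documents support this only for participants whose arrangement, re-dosing branch or usual medication differs between visits.
- A reader might take section 6.4.1.5 to say that separate-day tests are less bronchodilated. It does not. Its remark compares 2 with 4 inhalations of either agent in spirometry, not 4+4 after withholding with usual medication plus 2+2. All the conditions are post-bronchodilator.
- A reader might infer that baseline-to-Year-1 change is the only intermediate outcome for Aim 2. Section 7.4.3 offers it as an example, alongside presence or absence of a marker at Year 1, and section 3.1.2 also allows markers that change with exacerbations.
- It is tempting to set an assumed bias against the 0.20 SD in section 7.1. That figure concerns FEV1, measured after a fixed dose, and says nothing about CT. Nor do the documents show that sicker participants split their visits more often.
- Section 7.3 defers detailed analysis plans, and section 6.4.4.3 defers CT detail to the Imaging MOP, so adjustment for the condition may be planned elsewhere.

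The last point meets the concern only in part. A covariate cannot create matched pairs after the scans are done, and if arrangement happens to follow severity, adjustment could remove real signal. The repeatability study in section 9.2.2.6.1 (100 volunteers, CT included) can describe measurement error but does not remove a mismatch from anyone's change score.

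**Conclusion.** The point holds in a limited form. Followed as written, the protocol lets a participant's two CT scans be taken under different bronchodilator conditions, while matching scan dose between the same two scans. For participants whose arrangement differs, change in air trapping and airway dimensions can be confounded by the condition. The same applies, with less force, to the walk.

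The size is unknown. It depends on how many participants switch, whether switching runs one way, and how large the effect is, none of which the documents give. The assumed values above range from negligible (correlations multiplied by 0.998) to modest (a factor of 0.943, or a mean shift of 0.15 SD). They take an effect of 0.1 to 0.5 SD and independence between visits; persistent arrangements would reduce the share switching. This is a cheap improvement to the design, not a defect that invalidates the CT analyses.

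**What to change.** 1. Reconcile the same-day and separate-day conditions in sections 6.4.1.4 and 6.4.4.3 with the rationale in section 6.4.1.5, or state why they may differ for CT and walk. This review prefers no dose or withholding rule.
2. Beside the scan-dose rule in section 6.4.4.3, add that, where feasible, the Year 1 CT is scheduled in the same arrangement relative to spirometry as that participant's baseline CT. Say the same for follow-up walks.
3. Record at each visit whether the test was same-day or separate-day and which Table 4 branch applied, where the forms do not already capture it.
4. In analyses of CT or walk change, include the arrangement at each visit as a covariate, and repeat the analysis in participants whose arrangements match.

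The cost is one scheduling instruction, a variable derived from dates and dosing times, one covariate term and one sensitivity analysis. The drawback is slightly less scheduling flexibility at follow-up, which the words on feasibility limit.
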